7. STATISTICAL METHODS AND DETERMINATION OF SAMPLE SIZE

7.1 NULL AND ALTERNATIVE HYPOTHESES

Statistical testing is not planned for this trial. All analyses will be descriptive in nature. The endpoints will be investigated in comparison to placebo, however it is not planned to test a statistical hypotheses with regard to these variables in a confirmatory sense. Instead, they will be described and evaluated by descriptive statistical methods.

7.2 PLANNED ANALYSES

7.2.1 General considerations

[figure not shown]
The analyses will be performed based on the following analysis sets:

- **Enrolled set (ES)** – this analysis set includes all patients having signed informed consent and who were eligible for inclusion into the trial. The ES will be used for analyses of patient disposition
- **Randomised set (RS)** – this analysis set includes all enrolled patients that were randomised to the trial medication. The RS will be used for demographic and baseline disease characteristics presentation
- **Treated set (TS)** – the treated set includes all patients who were randomised to the trial medication and were treated with at least one dose. The TS will be used for all safety analyses
- **Full analysis set (FAS)** – this analysis set includes all randomised patients who received at least one dose of trial medication and have a baseline measurement for the primary endpoint recorded. The FAS will be used for the efficacy analyses

Further analysis sets will be defined in the TSAP, if needed.

Efficacy analyses will be performed based on the planned treatment (i.e. the treatment assignment at randomisation). Safety analyses will be based on the actual treatment received at the randomisation visit.

Unless otherwise stated, baseline is defined as the latest measurement before the first trial medication intake.

7.2.2 Handling of intercurrent events

The expected intercurrent events of interest in this trial are:

- use of the following restricted concomitant therapy:
 - NO-sGC-cGMP pathway activating therapies like NO-donors (e.g. glyceryl trinitrate, isosorbide di- or mono-nitrate, molsidomine), PDE-5-inhibitors (e.g. sildenafil, tadalafil, and vardenafil), non-specific PDE inhibitors such as dipyridamole and theophylline, or sGC-stimulators (e.g. riociguat)
- new onset of / dose change in existing NSBB / carvedilol concomitant therapy
- occurrence of a decompensation event

All intercurrent events will be handled according to the hypothetical approach as defined in ICH E9 (R1), to perform treatment comparison as if all patients took randomised treatment. Each analysis will reference the strategy for handling intercurrent events that it will be estimating. The estimand for each main analysis in this CTP is the combination of the relevant detailed clinical objective from Section [2.1](#) and this strategy.

Handling of the intercurrent events that are not listed above will be decided by the blinded review and will be documented in the TSAP.

7.2.3 Primary objective analyses

For the primary endpoint (refer to Section [2.1.2](#)), a restricted maximum likelihood (REML) based approach using a mixed model with repeated measurements (MMRM) will be used to obtain adjusted means for the treatment effects. The analysis will include the fixed, categorical effects of treatment at each visit, use of NSBBs or carvedilol (yes / no) at baseline

(refer to Sections [3.1](#) and [3.2](#)), and the fixed continuous effects of baseline HVPG at each visit. Visit will be treated as the repeated measure with unstructured covariance structure to model the within-patient measurements. The Kenward-Roger approximation will be used to estimate denominator degrees of freedom and adjust standard errors. The analysis will only be used for estimation of treatment effects without performing statistical tests. The analysis will be based on the FAS. Patients will be analysed according to the stratum to which they belong (regardless of any mis-assignment to treatment based on identification of the wrong stratum), as such an error occurs before randomisation and is therefore consistent with regulatory guidance. Procedures to follow if the analysis fails to converge will be described in the TSAP.

7.2.4 Secondary objective analyses

Unless otherwise stated, only descriptive statistics will be presented for the secondary endpoints defined in Section [2.1.3](#).

7.2.6 Safety analyses

Safety analyses will be descriptive in nature and follow BI standards, including (but not limited to): AEs, SAEs and AESI. AEs will be coded using the Medical Dictionary for Drug Regulatory Activities (MedDRA). Standard BI summary tables and listings will be produced. All AEs with an onset between start of treatment and end of the REP (refer to Section [1.2.1](#)) will be assigned to the on-treatment period for evaluation.

[figure not shown]
Safety analyses will be done by “treatment at onset” principle. All treated patients will be included in the safety analysis (TS). In general, safety analyses will be descriptive in nature and will be based on BI standards. No hypothesis testing is planned.

Statistical analysis and reporting of AEs will concentrate on treatment-emergent AEs, i.e. all AEs occurring between start of treatment and end of the REP. AEs that start before first trial medication intake and deteriorate under treatment will also be considered as ‘treatment-emergent’.

Frequency, severity, and causal relationship of AEs will be tabulated by system organ class and preferred term after coding according to the current version of the MedDRA at DBL.

Laboratory data will be analysed both quantitatively as well as qualitatively. The latter will be done via comparison of laboratory data to their reference ranges. Values outside the reference range, as well as values defined as clinically relevant, will be summarised. Treatment groups will be compared descriptively with regard to distribution parameters as well as with regard to frequency and percentage of patients with abnormal values or clinically relevant abnormal values.

Vital signs, physical examinations, or other safety-relevant data observed at screening, baseline, during the course of the trial and at the end-of-trial evaluation will be assessed with regard to possible changes compared to findings before start of treatment.

7.2.8 Interim analyses

An interim analysis is planned after the first 60 patients (20 per treatment group) have completed the first 8 weeks of treatment and the HVPG procedure. All available data at this stage will be analysed in the same way as is planned for the final analysis with the only exception of the primary endpoint and one of the secondary endpoints. The primary endpoint will not be analysed since the focus is the week 8 time point for the interim analysis. If applicable, the secondary endpoint defined as “percentage change in HVPG from baseline (measured in mmHg) after 8 weeks of treatment” will be analysed using an analysis of covariance (ANCOVA) model with treatment and baseline HVPG. This model will only be used to estimate treatment effects, no comparison via statistical testing will be performed.

The extent of the safety analyses will be to ensure that the trial is being conducted safely.

The interim analysis will be performed by an independent statistics and programming team within BI. The results of the interim analysis will be used internally and individuals involved in the conduct of the trial will not be made aware of the results. There will be no changes of the design of the trial because of this interim analysis and no stopping rules apply. For this interim analysis an interim analysis SAP and an interim analysis logistics plan will be developed, including a list with individuals and roles who will have access to unblinding information.

An external DMC will be implemented, with tasks and administrative details as briefly described in Section [8.7](#). Full details will be specified in the DMC charter. The primary role of the DMC is the ongoing evaluation of safety; the DMC will be informed about the results of the interim analysis.

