Following randomisation patients will begin the intake of trial medication and will enter a dose-titration period. All patients in all treatment groups will start this period on a dose of ██████████ *BID* 685509 or matching placebo. If the dose is tolerated one week later (at Visit 3, day 8), the dose for all treatment groups will be up-titrated to ██████████ *BID* 685509 or matching placebo. For the ██████████ *BID* dose treatment group only, and if the dose is tolerated, a second up-titration to ██████████ *D* 685509 or matching placebo will occur after another week (at Visit 4, day 15). However, as this is a double-blind trial, patients randomised both to ██████████ *BID* 685509 and to placebo will also have a dose-titration at Visit 4 (day 15). For these treatment groups the dose-titration will be a pseudo-titration (i.e. those randomised to ██████████ *BID* BI 685509 will remain on that dose, and those randomised to placebo will remain on placebo). Following the dose-titration period, and if the dose is tolerated, patients will remain on their maximum planned maintenance dose for the remainder of the treatment period until they reach the End of Treatment (EoT) visit and 24 weeks of treatment. If the dose is not tolerated, trial medication may be interrupted or the dose can be reduced / down-titrated.

The ultrasound and ██████████ of the liver and spleen, and the HVPG measurement will be repeated during the randomised treatment period (refer to Figure [3.1: 1](#)).

After approximately 60 randomised patients have completed Visit 7 (week 8 of treatment) and the HVPG procedure, there will be an interim analysis. Recruitment will continue whilst the analysis takes place. The results of the interim analysis will establish short-term efficacy and allow assessment of an internal development milestone. For further details regarding the interim analysis refer to Section [7.2.8](#).

After the 24 week randomised treatment period all patients will enter a 4 week follow-up period without trial medication. The patient's participation in the trial will be complete when they have performed the last planned visit (i.e. End of Study [EoS], 4 weeks after EoT).

[figure not shown]

Figure 3.1: 1 Trial design schematic

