3.3.2 Inclusion criteria

1. Signed and dated written informed consent in accordance with ICH-GCP and local legislation prior to admission to the trial
2. Male or female who is ≥ 18 (or who is of legal age in countries where that is greater than 18) and ≤ 75 years old at screening (Visit 1a)
3. Clinical signs of CSPH as described by either one of the points below. Each trial patient must have a gastroscopy during the screening period (Visit 1b) or within 6 months prior to screening (Visit 1b). For further details refer to Section [5.2.5.2](#)
 - documented endoscopic proof of oesophageal varices and / or gastric varices at screening (Visit 1b) or within 6 months prior to screening (Visit 1b)
 - documented endoscopic-treated oesophageal varices as preventative treatment
4. CSPH defined as baseline HVPG ≥ 10 mmHg (measured at Visit 1c), based on a local interpretation of the pressure tracing (refer to Section [5.1.1](#) for further details)
5. Diagnosis of compensated alcohol-related cirrhosis. Diagnosis must be based on histology (historical data is acceptable) or on clinical evidence of cirrhosis (e.g. platelet count $< 150 \times 10^9/L$ [$150 \times 10^3/\mu L$], nodular liver surface on imaging or splenomegaly)
6. Abstinence from significant alcohol misuse / abuse for a minimum of 2 months prior to screening (Visit 1a), and the ability to abstain from alcohol throughout the trial (both evaluated based on Investigator judgement)
7. Willing and able to undergo HVPG measurements per protocol (based on Investigator judgement)
8. If receiving statins must be on a stable dose for at least 3 months prior to screening (Visit 1b), with no planned dose change throughout the trial
9. If receiving treatment with NSBBs or carvedilol must be on a stable dose for at least 1 month prior to screening (Visit 1b), with no planned dose change throughout the trial
10. WOCBP¹ must be ready and able to use highly effective methods of birth control per ICH M3 (R2) that result in a low failure rate of less than 1% per year when used consistently and correctly from the randomisation visit (Visit 2) until 7 days after the last treatment in this trial. The patient must agree to periodic pregnancy testing during participation in the trial. Refer to Section [4.2.2.3](#) and the patient information for a list of contraception methods meeting these criteria

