7.4 RANDOMISATION

BI will arrange for the randomisation and the packaging and labelling of trial medication. The trial will be performed as a double-blind design with respect to placebo and the two dose groups of active BI 685509. Patients will be randomised in blocks to one of the three treatment groups in a 1:1:1 ratio. The randomisation will be stratified by use (or not) of NSBBs or carvedilol (refer to Section [3.1](#)).

The randomisation list will be generated using a validated system, which involves a pseudo-random number generator so that the assigned treatment will be reproducible but at the same time non-predictable. The block size will be documented in the CTR. Access to the codes will be controlled and documented.

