7.4 PRIMARY OBJECTIVE ANALYSIS

7.4.1 Main analysis

The primary endpoint will be analysed through a MMRM model in combination with the primary estimand of handling ICEs (see [Section 6.3](#)). The FAS will be used for the analysis: the patient set includes all patients who had at least one evaluable baseline HVPG measurement. The missing data will not be imputed. Instead, the MMRM will handle missing data based on a likelihood method under the “missing at random” assumption.

For the MMRM model, treatment at each visit, use of NSBBs or carvedilol (yes / no) at baseline, and baseline HVPG at each visit will be used as covariates. Refer to Section 7.2.3 of the CTP for a detailed description of the statistical analysis for the percentage change from baseline in HVPG after 24 weeks of trial treatment.

The adjusted estimate of mean percentage change from baseline in HVPG at 24 weeks and its standard error will be obtained from MMRM for the placebo and treatment groups. The 95% CI will be provided for adjusted mean effect of each treatment group as well as the comparison with placebo.

SAS code for **the MMRM model** will be based on the following structure:

```
PROC MIXED DATA=alldat cl method=reml;  
  CLASS visit trt subject;  
  MODEL chg = base*visit visit*trt stra / ddfm=kr s CL; REPEATED visit / subject=  
  subject type=un r rcorr;
```

```
LSMEANS visit*trt /pdiff=all om cl alpha=0.05 slice=visit;
```

```
RUN;
```

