7.5.2 Secondary objective analysis

The secondary endpoints for this study are described in CTP Section 2.1.3.

For the secondary endpoint of percentage change in HVPG after 8 weeks of treatment, the analysis of covariance (ANCOVA) will be used. The analysis will be performed on the FAS with treatment assignment as randomized and include on-treatment HVPG only. If a patient misses the Week 8 visit, the missing data will not be imputed.

This model will include treatment and use (or not) of NSBBs or carvedilol as fixed classification effects and baseline HVPG as a linear covariate. The random error is assumed to be normally distributed with mean 0 and variance σ^2 . The analysis will only be used for estimation of treatment effects without performing statistical tests.

For other secondary endpoints, only descriptive statistics will be presented.

For the occurrence of decompensation events, categories are defined in Table [7.5.2:1](#)

Table 7.5.2:1 Categories for decompensation events

Categories	Definition
Ascites	PT - 'Ascites' PT - 'Bacterascites' PT - 'Haemorrhagic ascites'
Variceal haemorrhage	PT - 'Oesophageal varices haemorrhage' PT - 'Oesophageal haemorrhage' PT - 'Bleeding varicose vein' HLT - 'Gastric and oesophageal haemorrhages' HLT - 'Non-site-specific gastrointestinal haemorrhages'
Hepatic encephalopathy	PT - 'Hepatic encephalopathy' PT - 'Coma hepatic' PT - 'Hyperammonaemic encephalopathy' PT - 'Hyperammonaemic crisis'
Other	PT - 'Cardiohepatic syndrome' PT - 'Hepatorenal syndrome' PT - 'Hepatorenal failure' PT - 'Hepatic hydrothorax' PT - 'Hepatopulmonary syndrome'

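### The interim Week-8 ANCOVA leaves out NSBB/carvedilol use, the randomisation stratum that the primary MMRM and the SAP's final Week-8 ANCOVA both include

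*Protocol*

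**What the plan says.** - **Randomisation (protocol 7.4).** "The randomisation will be stratified by use (or not) of NSBBs or carvedilol". No other factor is named. Protocol 3.2 explains the choice: these drugs can affect how far HVPG falls.
- **Primary analysis.** The MMRM in protocol 7.2.3 includes "treatment at each visit, use of NSBBs or carvedilol (yes / no) at baseline" together with baseline HVPG by visit. SAP 7.4.1 repeats this: "use of NSBBs or carvedilol (yes / no) at baseline, and baseline HVPG at each visit will be used as covariates".
- **Final Week-8 analysis (SAP 7.5.2).** "This model will include treatment and use (or not) of NSBBs or carvedilol as fixed classification effects and baseline HVPG as a linear covariate".
- **Interim Week-8 analysis (protocol 7.2.8).** With 60 patients, 20 per group, the same endpoint, if applicable, "will be analysed using an analysis of covariance (ANCOVA) model with treatment and baseline HVPG". The model is for estimation only. Missing Week-8 HVPG is not imputed (protocol 7.3).
- **Use of the interim (protocol 3.1).** "The results of the interim analysis will establish short-term efficacy and allow assessment of an internal development milestone".
- **Further detail (protocol 7.2.8).** "an interim analysis SAP and an interim analysis logistics plan will be developed". That interim SAP is not among the documents.

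**The concern.** A factor judged important enough to stratify on would normally be in every model of the same outcome. Here it is missing from one model only. If NSBB/carvedilol use predicts percentage change in HVPG after adjustment for baseline, its variance stays in the interim residual. Stratified randomisation has already removed most of that variance from the treatment comparison, so the model-based standard error overstates the true uncertainty, and any interval built from it is too wide.

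There are two lesser consequences. The interim and final Week-8 estimates would not come from the same model. Any imbalance in the stratum among patients with Week-8 HVPG would also go uncorrected.

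What is at stake is the quality of the one modelled efficacy estimate that protocol 7.2.8 names for the interim. It feeds an internal milestone, and the DMC is informed of the interim results. No error rate is involved.

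**Working it through.** **Model terms side by side**

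| Analysis | Treatment | Baseline HVPG | NSBB/carvedilol |
|---|---|---|---|
| Primary MMRM (protocol 7.2.3, SAP 7.4.1) | by visit | by visit | yes |
| Final Week-8 ANCOVA (SAP 7.5.2) | yes | yes | yes |
| Interim Week-8 ANCOVA (protocol 7.2.8) | yes | yes | no |

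**The plan's own figures.** The plan gives no figure for the interim model. The SDs come from protocol 7.5, so that section was checked first. With SE = 27.5 × √(2/26) = 7.63 and a correlation between the two dose-placebo differences of (0.2 + 1)/2 = 0.6, the probability that at least one difference reaches 15 points is 95.2% for 25/23/0; the protocol states 94.95%. The other five entries of Table 7.5: 1 also reproduce to within 1 point.

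**Inputs for the interim**

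- n = 60, 20 per arm (protocol 7.2.8).
- SD 27.5 or 33.0 points (protocol 7.5). These are Week-24 SDs; using them as the Week-8 residual SD within stratum is an assumption.
- Proportion of users p = 0.3 to 0.7, and gap g = 0 to 20 points in mean HVPG change between users and non-users. Both are assumptions, as the documents give neither.
- Residual degrees of freedom: 60 − 4 = 56 without the stratum, 60 − 5 = 55 with it.

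**Formulas, strata balanced across arms**

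- Expected residual variance without the stratum: V = SD² + 60·p(1−p)·g²/56. With the stratum: SD².
- 95% half-width: t(0.975, df) × √(variance × 2/20), with t = 2.003 (56 df) or 2.004 (55 df).

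Worked case, SD 27.5, p = 0.5, g = 20: V = 756.25 + 60 × 0.25 × 400/56 = 756.25 + 107.14 = 863.39. Half-width without the stratum = 2.003 × √86.339 = 18.61. With it, 2.004 × √75.625 = 17.43. The ratio is 1.068.

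**Results at p = 0.5 (95% half-width, points)**

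| Gap | SD 27.5, without v with | Excess | SD 33.0, without v with | Excess |
|---|---|---|---|---|
| 0 | 17.42 v 17.43 | -0.04% | 20.90 v 20.91 | -0.04% |
| 10 | 17.73 v 17.43 | 1.71% | 21.16 v 20.91 | 1.18% |
| 20 | 18.61 v 17.43 | 6.81% | 21.91 v 20.91 | 4.76% |

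At p = 0.3 or 0.7 and SD 27.5, the excess is 1.44% at a gap of 10 and 5.74% at 20.

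**Other reading of the SD.** If 27.5 is taken as the SD before the stratum is removed, the residual variance with the stratum is 27.5² − p(1−p)g². The SE of a dose-placebo difference is then 8.70 without the stratum. With it, the SE is 8.55 to 8.58 at a gap of 10 (1.4 to 1.7% smaller) and 8.10 to 8.20 at a gap of 20 (5.7 to 6.9% smaller). The conclusion is the same.

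**Simulation.** There were 4,000 trials per setting, with stratified permuted blocks (block size 6 assumed). Mean estimates from the two models agreed within 0.03 points. Coverage was 94.4 to 96.5% without the stratum and 94.3 to 95.7% with it. In a separate run with 27.5 as the total SD, p = 0.5 and g = 20, the model without the stratum reported a mean SE of 8.78 against an empirical SD of 8.33; the empirical SD with the stratum was 8.30. So the estimate itself is almost equally precise under either model, and omission mainly inflates the reported SE.

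**Imbalance.** Stratified blocks limit imbalance, but the interim uses observed Week-8 data only, and HVPG is not required at early discontinuation (protocol 6.2.2.1). As an illustration, 12 v 8 users among 20 per arm with a 10-point gap would shift the difference by (4/20) × 10 = 2 points.

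**The case against.** 1. **The interim SAP is not available** and may already contain the term. This stands as a limit: the point concerns the model written in protocol 7.2.8, not what was or will be run.
2. **The protocol is consistent with itself on this endpoint.** Section 7.2.8 declares the Week-8 analysis an exception to the final plan, and 7.2.4 makes secondary endpoints descriptive unless otherwise stated. The mismatch arises because the later SAP adds a Week-8 ANCOVA in 7.5.2 while stating in its section 4 that nothing has changed. That explains why 7.2.8 needs its own model, but not why the model drops the stratum.
3. **Nothing in the trial's conduct depends on it.** There is no test, stopping rule or design change, and those running the trial do not see the results. This is correct, and it is why the point is minor.
4. **The effect may be negligible.** Users must have been on a stable dose for at least 1 month before Visit 1b, with no planned change (protocol 3.3.2), so baseline HVPG already reflects the drug. A 20-point gap is close to the whole drug effect of 21 to 25 points in the positive scenarios of protocol 7.5 and should be read as an extreme. At 10 points the cost is 17.73 − 17.43 = 0.30 points on a half-width, and at zero the simpler model is very slightly narrower. All of this stands.
5. **The SDs are Week-24 figures used at Week 8.** This is also true, and the half-widths are illustrative for that reason.

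**Conclusion.** The concern holds as a minor point. NSBB/carvedilol use is missing from the interim Week-8 model only, and neither document says why. With balanced strata there is no bias and no undercoverage; the reported interval is at worst conservative. Over the assumed ranges the change in half-width runs from -0.04% to +6.8%, and it stays at or below 1.7% for gaps of 10 points or less. Those sizes rest on an assumed proportion of users, an assumed gap and Week-24 SDs applied at Week 8. The case for the change is consistency with the trial's own randomisation and with its final Week-8 model, at almost no cost, and not the repair of a material error.

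**What to change.** In the interim analysis SAP, use the SAP 7.5.2 model: treatment and NSBB/carvedilol use (yes/no) as fixed effects and baseline HVPG as a covariate. If the factor is left out deliberately, state why.

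The cost is one model term and one of 56 residual degrees of freedom. The stratum is already recorded for randomisation. The wording of protocol 7.2.8 can be aligned at an amendment made for other reasons, since amendments need ethics committee and authority approval (protocol 8.1). If the interim SAP already includes the term, only that wording needs attention. The documents do not say whether the interim has been run; if it has, report the stratum-adjusted Week-8 estimate beside the one produced.
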